6.13 Dataset

A realistic data set will be fundamental to the success of the investigation. This dataset will include the following:

All patients:

- Age (continuous, numerical)
- Sex (categorical, nominal)
- Weight (continuous, numerical)
- Height (continuous, numerical)
- Co-morbidities (categorical, nominal)
- Chronic medication (categorical, nominal)
- ASA Physical Status (categorical, ordinal)
- Severity of surgery (categorical, nominal)
- Type of surgery (categorical, nominal)
- Hemacue Hb

All anaemic patients

- Pre-intervention Hb (continuous, numerical)

- Pre-intervention MCV (continuous, numerical)
- Pre-intervention ferritin (continuous, numerical)
- Pre-intervention TSAT (continuous, numerical)
- Pre-intervention CRP (continuous, numerical)
- Pre-intervention reticulocyte Hb content (continuous, numerical)
- Syrup or tablet prescribed (categorical, nominal)
- Actual dose of elemental iron prescribed ($\text{mg}^{-1} \cdot \text{kg}^{-1} \cdot \text{day}^{-1}$)

All patients with IDA

- Post-intervention Hb (continuous, numerical)
- Post-intervention MCV (continuous, numerical)
- Post-intervention ferritin (continuous, numerical)
- Post-intervention TSAT (continuous, numerical)
- Post-intervention CRP (continuous, numerical)
- Post-intervention reticulocyte Hb content (continuous, numerical)
- Days of oral iron treatment (continuous, numerical)

6.14 Case record forms

Whole cohort (1110 patients)

An Outpatient CRF will be completed for every enrolled patient (Appendix F). This will be completed by the research nurse at each site.

IDA cohort

A Telephonic Survey CRF will be completed on a weekly basis for up to 3 months for every patient (Appendix G). This will be completed by the research assistant.

A Surgical Admission CRF will be completed on admission for surgery by the surgical team (Appendix H).

6.15 Collection and storage of blood samples

EMLA will be applied by the research nurse at the outpatient clinic. These patients will then have venepuncture performed by the on-site hospital phlebotomist. These samples will include an EDTA tube for FBC, and reticulocyte Hb content, and a gold top tube (serum separator) for C-reactive protein, ferritin, and transferrin saturation content. These samples will be labelled and stored in accordance with standard operating procedure.

6.16 Monitoring medical adherence

Few validated medical adherence surveys have been developed for the paediatric population and these are limited to asthma, HIV/AIDS, epilepsy, ADHD, and diabetes³⁴. Therefore, medical adherence will be defined as the following:

Number of days the patient takes the iron supplement/number of days the patient is prescribed to take the iron supplement.

This will be assessed on a weekly basis via the telephonic survey.

The parent or legal guardian will also be asked to bring any unused iron supplements when their child is admitted for surgery. A pill count and a count of remaining iron syrup will be done to cross-reference against the reported doses taken.

6.17 Safety reporting

All study participants enrolled to take oral iron supplements will be monitored via a weekly telephonic survey for adverse events (AE). The parent or legal guardian will also be given contact details for the research nurse who will be available to be contacted with any concerns.

Serious Adverse Events (SAE) including death, life-threatening, requiring inpatient hospitalisation or prolongation of existing hospitalisation, results in persistent or significant disability/incapacity, are extremely unlikely given the safety profile and well-established use of oral iron supplementation in the paediatric population. Should a SAE or Serious ADR occur this will be reported to the sponsor (University of Cape Town) within 24 hours, and within 7 days to the UCT HREC. SAE & Serious ADR will be collected on a specially designed form (Appendix H).

Non-serious adverse events (AE), will be documented clearly on the CRF for the telephonic surveys. Common side-effects will be asked about specifically, these include vomiting, nausea, stomach cramps or bloating, heartburn, constipation, and diarrhoea. Should the patient suffer from any of these side-effects they will be given telephonic advice on the management options as per the telephonic survey and referred to the research nurse or clinician investigators where appropriate. Any AE, illness, or clinically significant abnormal laboratory values, actions taken, and treatments provided will be clearly documented. It will also be recorded if the individual withdraws, and this will include the reason for withdrawal if the participant is willing to supply one. If the Hb $<7.0\text{g.dl}^{-1}$ on the formal laboratory results, the parent or legal guardian must be contacted and referred for further medical investigation and treatment.

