6.8 Ensuring adequate resources

To conduct a sound and valid study the investigators will ensure to the best of their ability that the following criteria are met:

- 1) Reasonable potential to recruit 1110 individuals to the study over a cumulative 9-month period.
- 2) An appropriate amount of time to complete recruitment, intervention, and data collection (9 months).
- 3) An adequate supply of suitably qualified staff at each facility including:
 - a) Appointed research nurse at each research site able to carry out the following responsibilities 3 days per week:
 - 08:00 to 10:00
 - Checking National Health Laboratory Services Results (NHLs) for blood tests at outpatient clinic
 - Telephonic follow-up with recruited patients to discontinue iron supplementation if they do not meet criteria for IDA
 - 10:00 to 16:00
 - Recruitment of patients for study
 - Obtaining written informed consent and assent where appropriate
 - Performing finger-prick Hb (Hemacue)
 - Applying EMLA for venepuncture for anaemic patients

Giving drug script signed by clinic doctor for oral iron supplementation ± deworming medication for collection at the hospital pharmacy

- b) Appointed research assistant for all sites to complete weekly telephonic survey for all IDA patients assessing medical adherence and side-effects, referring onto study nurse or doctor where appropriate.
- 3) Appropriate training on the study protocol, about any investigational product and about their duties to allow the staff to carry out their tasks safely and effectively.
- 4) Appropriate supervision of any individual or group to whom the investigator assigns trial-related duties at the trial site
- 5) Assurance that any person or party retained to perform trial-related duties is suitably qualified to perform those duties.

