6.10 Supplemental iron dosing regimen

All patients diagnosed with anaemia on the point of care Hemacue test will be given an oral iron supplement to take every day prior to surgery for a maximum of 3 months.

The recommended treatment dose of elemental iron for IDA is $3-6\text{mg}^{-1}\text{kg}^{-1}\text{day}^{-1}$ ³³. This can be increased to $12\text{mg}^{-1}\text{kg}^{-1}\text{day}^{-1}$. The recommendation from Red Cross War Memorial Hospital Pharmacy is that iron syrup is preferred in children up to 4 years old or in older children unable to take tablets (Table 1).

Table 1. Ferrous gluconate (350mg/5ml) Elemental Iron 8mg/ml Dosing

Weight (kg)	BD dose (mL)
5	2
6	2.5
7	2.5
8	3
9	3.5
10	4
11	4
12	4.5

13	5
14	5.5
15	5.5
16	6
17	6.5
18	7
19	7
20	7.5

If the child can take iron tablets the recommendation is possible to prescribe a dose at increments of $\frac{1}{2}$ tablet (37.5mg) (Table 2).

Table 2: Ferrous Fumarate/Folic acid - Elemental iron 65mg tablets Dosing

Weight Range	Tablets*
10 to 14 kg	1.0
>15 to 20 kg	1.5
>20 to 30 kg	2.0
>30kg	3.0

*Dose to be split into BD

Table 3: Ferrous sulphate - Elemental iron 55mg tablets Dosing

Weight Range	Dose
20 to < 27 kg	1 tab bd
27 to < 37 kg	2 tab am/1 tab pm
37 kg and above	2 tab bd

Based on this the dose range when prescribing tablets for patient weight range 10 to 59 kg is 2.2 to $6.5 \text{ mg}^{-1}\text{kg}^{-1}\text{day}^{-1}$. The oral iron supplementation will be dispensed the same day as the outpatient clinic appointment, with clear verbal instructions on how to take the medication and potential side-effects. The parent or legal guardian will also be given a patient information leaflet, with information on anaemia, how to take the medication, potential side-effects, and who to contact should they have any further questions or concerns (Appendix D).

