6.12 Research procedures, data collection and collation

At recruitment phase

Eligible patients will be screened for anaemia with a finger-prick bedside Hemacue test at outpatient clinic. If the patient meets the WHO criteria for anaemia EMLA cream will be applied to potential sites for venepuncture and the patient will then be sent to the pathology laboratory for venepuncture with a request form for tests that will include laboratory full blood count (FBC), ferritin, transferrin saturation (TSAT), C-reactive protein (CRP), and reticulocyte Hb content. Patients who have not been dewormed within the last 6 months will be treated with mebendazole or albendazole as per the South African guidelines³³.

The patients age, weight, height, co-morbidities, ASA physical status, planned surgical procedure, planned date of surgery, severity of surgery, and type of surgery will be recorded. They will also be informed that they will be contacted telephonically once a week by the research assistant to enquire about compliance with the medication and enquire about any side-effects with the medication. The telephonic contact details will be confirmed by the research nurse and documented on the paper Outpatient CRF.

At home

The laboratory blood test results will be reviewed within 48 hours to diagnose those patients who meet the criteria for IDA. Any patients who do not meet the criteria will be contacted via telephone by the research nurse to instruct them to stop taking the iron supplementation and to bring the remaining iron supplementation with them to their next hospital visit. These patient folders and results for those patients not meeting the criteria for IDA will be reviewed by the appropriate surgical team to decide on appropriate ongoing management and further investigations which will be individualised to the patient.

For those patients meeting the criteria for IDA and continuing the oral iron supplementation, the parent or legal guardian will be contacted weekly to complete a short telephonic survey on compliance with the medication, side-effects, and to answer any questions or concerns they may have.

At time of Surgery

Repeat laboratory FBC at time of routine preoperative bloods if part of standard care.

Repeat ferritin, CRP, TSAT ± FBC whilst under anaesthesia prior to start of surgery.

Data collection

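### The protocol disagrees with itself on who gets the weekly adverse-event survey, and children who take iron but prove not to have IDA have no scheduled side-effect enquiry

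*Combined protocol and SAP*

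**What the plan says.** **Who receives iron.** Section 6.10: "All patients diagnosed with anaemia on the point of care Hemacue test will be given an oral iron supplement to take every day". Dispensing is on the day of the clinic visit. Laboratory results are reviewed afterwards, within 48 hours according to 6.12 and within 48-76 hours according to 6.1. Children who do not meet the IDA criteria are then telephoned by the research nurse and told to stop.

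**Sections that imply a survey for everyone given iron.**
- 6.17: "All study participants enrolled to take oral iron supplements will be monitored via a weekly telephonic survey for adverse events (AE".
- 6.12, recruitment paragraph: "They will also be informed that they will be contacted telephonically once a week by the research assistant to enquire about compliance with the medication". The same sentence goes on to side-effects. It applies before IDA status is known and carries no IDA restriction.

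**Sections that restrict the survey to IDA.**
- 6.8 gives the research assistant the task to "complete weekly telephonic survey for all IDA patients assessing medical adherence and side-effects".
- 6.12, At home: "For those patients meeting the criteria for IDA and continuing the oral iron supplementation, the parent or legal guardian will be contacted weekly".
- 6.14: "A Telephonic Survey CRF will be completed on a weekly basis for up to 3 months for every patient". This sentence stands under the heading for the IDA cohort.

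**Where non-serious events are recorded.** 6.17: "Non-serious adverse events (AE), will be documented clearly on the CRF for the telephonic surveys".

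**The concern.** Dosing starts on the finger-prick result, while the operational sections start active safety follow-up only on the laboratory result. A child who takes iron and is then found not to have IDA falls between the two. The stop call is described as an instruction to stop and to bring back what is left. No side-effect question is specified for it. The form that holds non-serious events belongs to the IDA cohort. The dataset in 6.13 lists days of oral iron for IDA children only, so exposure in the others is not captured either.

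Three things are at stake. Sites cannot tell from the text whom to survey, or where to write down a non-serious event in a child told to stop. Families may be told at recruitment to expect weekly calls that the later sections do not provide. And any side-effect information will come only from children who continued iron, although the pathway being piloted doses every anaemic child.

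**Working it through.** **Step 1. The contradiction.** It needs no arithmetic.

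| Section | Who gets the weekly survey |
|---|---|
| 6.17 | all participants enrolled to take iron |
| 6.12, recruitment | no IDA restriction stated |
| 6.8 | IDA patients |
| 6.12, At home | IDA patients continuing iron |
| 6.14 | form listed under the IDA cohort |

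Section 6.12 is therefore split within itself.

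**Step 2. Reproduce the plan's figures.**
- Site table in 6.7, screened: 310 + 150 + 150 + 5 × 100 = 1110. Expected IDA: 12 + 6 + 6 + 5 × 4 = 44. Both totals agree with the table.
- Sample size section: 420 × 0.90 × 0.462 = 174.6, against the stated figure of about 176.
- Power analyses section: 176 × 0.2, 0.3, 0.4 and 0.5 gives 35, 53, 70 and 88 IDA children, as tabulated.

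**Step 3. Share of dosed children outside the survey** = 1 − (IDA children / anaemic children).

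| Source of figures | Dosed | IDA | Outside survey |
|---|---|---|---|
| 6.7 table with 46.2% anaemia | 1110 × 0.462 = 513 | 44 | 469 (91.4%) |
| Same, less 10% dropout | 462 | 44 | 418 (90.5%) |
| Power section, IDA share 20% | 176 | 35 | 141 (80%) |
| Power section, 30% | 176 | 53 | 123 (70%) |
| Power section, 40% | 176 | 70 | 106 (60%) |
| Power section, 50% | 176 | 88 | 88 (50%) |

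The two sources do not agree. 44/513 is 8.6% IDA among anaemic children, below the lowest share in the power table. Shares of 20% to 50% of 513 would be 103 to 256 IDA children, not 44.

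**Step 4. Share of iron-days.** Assumptions: children told to stop take iron for 2 to 3.17 days (48 to 76 hours); IDA children take it for 42 to 90 days (six weeks to three months). Share in stopped children = n₁d₁ / (n₁d₁ + n₂d₂).
- 469 stopped, 44 IDA, lowest: 469 × 2 / (469 × 2 + 44 × 90) = 938/4898 = 19%.
- Same counts, highest: 469 × 3.17 / (469 × 3.17 + 44 × 42) = 45%.
- Power section, lowest (88 and 88): 88 × 2 / (88 × 2 + 88 × 90) = 2%.
- Power section, highest (141 and 35): 141 × 3.17 / (141 × 3.17 + 35 × 42) = 23%.

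Sensitivity: if the stop call slipped so that exposure lasted 7 days, the 469 and 44 scenario would give 45% (against 90 days) to 64% (against 42 days). Delay is possible, because 6.8 has the nurse on these duties three days a week and the body text gives no procedure for a parent who is not reached.

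**The case against.** **6.17 can be read narrowly.** Being enrolled to take iron and monitored weekly fits children who stay on it, and a child stopped after two or three days would normally be off iron before a first weekly call. This reading is possible, but it does not sit easily with the unrestricted recruitment paragraph of 6.12. Even if it is accepted, children who took iron and stopped still have no scheduled enquiry, so the gap remains.

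**A reader might infer that nine in ten dosed children go without any adverse-event monitoring.** The documents do not support that. The nine-in-ten figure needs the 44 IDA children of 6.7 combined with 46.2% anaemia; the power section's shares give 50% to 80%. Parents hold the research nurse's contact details, serious-event reporting is not limited to IDA children, 6.17 has a general rule that any adverse event be documented, and the surgical team reviews the folders and results of non-IDA children. What is missing is a scheduled, active question and a named form.

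**Headcount overstates the safety gap.** This stands. On planned timing the exposure of these children is brief, and step 4 shows a much smaller share of iron-days.

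**The forms cannot be inspected.** This also stands. The CRFs appear only as appendix titles, so the statement is limited to the body text.

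**Side-effects are not a stated objective or outcome, and no adverse-event analysis is planned.** Correct. The primary haemoglobin comparison in IDA children is unaffected, and there is no case for one pooled side-effect rate over all dosed children, since it would mix a few days of exposure with many weeks.

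**Conclusion.** The point holds as an internal contradiction with a practical gap behind it. Sections 6.17 and 6.12 (recruitment) conflict with 6.8, 6.12 (At home) and 6.14 on who is surveyed. Children given iron who prove not to have IDA have no scheduled, active side-effect enquiry, and the body text names no form for their non-serious events.

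They are at least half of dosed children on every planning figure in the protocol: 50% to 80% on the power section's IDA shares, about 91% on the 6.7 table with 46.2% anaemia. This assumes that every finger-prick-anaemic child screened starts iron and that anaemia is as frequent as in the earlier cohort. On planned timing they hold 2% to 45% of iron-days across those scenarios, more if stop calls are late.

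The consequence is incomplete safety capture and unclear site instructions. It is not an absence of safety oversight, and it does not bias the primary result.

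**What to change.** 1. Reconcile 6.8, 6.12, 6.14 and 6.17 so that they state one rule on who receives the weekly survey, and align what families are told at recruitment.
2. Add the common side-effect questions already listed in 6.17 to the stop call that the research nurse is already due to make.
3. Record the answers as a single entry on the Telephonic Survey CRF. Section 6.14 needs to allow this for children outside the IDA cohort and to let the nurse complete it, since it currently assigns the form to the research assistant.
4. Extend the 6.13 item on days of oral iron to children told to stop.
5. Report any side-effects separately for children who stopped and children who continued, each with days of exposure, and not as one pooled rate.

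The cost is a few extra minutes on each stop call, plus minor wording in the CRF and protocol. No extra visit or blood sample is needed.

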5.10 Expected benefits to individual participants and potential societal benefits

As an individual the participant may benefit from the intervention by a direct increase in their haemoglobin levels. The impact of increased haemoglobin levels may translate to improved perioperative outcomes and reduced blood transfusion rates for the individual patient. Please note that the study is not designed to evaluate the impact of the intervention on these outcomes. The impact of treatment with iron may also have a positive impact on cognitive development, for the individual child, although again this study is not designed to assess this outcome.

The potential benefit to the wider community of children undergoing surgery in South Africa is a greater understanding of the efficacy and feasibility of oral iron as treatment for preoperative anaemia in children, and further insight into the optimal oral iron regimen.

5.10 Sample size calculation

How many patients will need to have a screening finger-prick Hb for the pilot study to be a representative of children undergoing noncardiac surgery with preoperative anaemia?

Secondary analysis of SAPSOS study found 46.2% patients were anaemic, using estimation for a single proportion with a specified precision and allowing for 10% drop out.

$$n = [p(1-p)z^2] / d^2$$

n: sample size

p: population proportion

z: 1.96, level of confidence, normal distribution

d: 0.05, acceptable margin of error

$$n = 0.46.(0.538)3.8416 / 0.0025 = 381.98$$

10% drop out rate: 38.2

Sample size: $382 + 38 = 420$

Given a sample size of 420 patients allowing for 10% drop-out approximately how many anaemic patients will be enrolled?

$$n = 420 * 0.90 * 0.462 \sim 176$$

[figure not shown]

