6.7 Recruitment and screening

Eligible subjects will be identified at routine surgical outpatient appointments. Paper informed consent will be obtained prior to a finger-prick screening haemoglobin (Hemacue) is performed, with translators where necessary, from the primary parent or legal guardian or legally authorised representative and included assent of the child where appropriate. Broadcasting through an appropriate hospital notice will inform the patients, their parents/guardians and the public that the hospital is participating in the study (Appendix C).

The total patients planned to be recruited for screening is 1110 patients and these will be divided across 7 sites:

Sites		Number of patients to be screened	Estimated number of patients with IDA
Western Cape		460	18
Red Cross War Memorial Children's Hospital		310	12
Tygerberg Hospital		150	6
KwaZulu-Natal		250	10
Inkosi Albert Luthlui Hospital		150	6
Greys Hospital		100	4
Gauteng		400	16
Steve Biko Hospital		100	4
Kalafong Hospital		100	4
Chris Hani Baragwanath Hospital		100	4
Charlotte Maxeke Johannesburg Academic Hospital		100	4
Total		1110	44

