5.10 Power analyses

What effect size could we expect to find statistically significant for the whole cohort given an estimated sample size of 176 patients?

Effect size for comparison between mean Hb pre and post intervention for whole cohort (matched pairs samples t-test) of 176 patients. Assuming data are normally distributed.

Sample size = 176, power = 80%, two-tailed significance 0.05

Effect size ~ 0.21

```
pwr.t.test(n = 176, d = NULL, sig.level = 0.05, power = 0.8,
type = "paired", alternative = "two.sided")
```

Paired t test power calculation

n = 176
d = 0.2123609
sig.level = 0.05
power = 0.8
alternative = two.sided

NOTE: n is number of *pairs*

What effect size could we expect to find statistically significant for the cohort of patients with IDA given an estimated sample size of 176 anaemic patients, if the incidence of IDA is unknown?**

IDA prevalence	IDA Sample size	Effect size (matched pairs samples t-test)	Effect size (Wilcoxon signed-rank test (matched pairs))
0,2	35	~0.5	~0.5
0,3	53	~0.4	~0.4
0,4	70	~0.34	~0.35
0,5	88	~0.3	~0.31

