5.11 Statistical analysis

Categorical variables will be reported as number and percentage. All patient and surgical characteristics will be compared between children with and without anaemia and comparing children with IDA versus anaemia of other cause using Pearson's chi-squared or Fisher's exact tests as appropriate. These will include age groups, sex, type of surgery (general, orthopaedic, ENT, plastics, other), severity of surgery as per SAPSOS definitions (mild, moderate, severe), severity of anaemia as per WHO definitions (mild, moderate, severe).

Normal distribution of continuous variables will be determined by Shapiro-Wilk testing and summarised appropriately as means \pm standard deviation or as medians \pm interquartile range (IQR). All patient and surgical characteristics will be assessed with parametric testing (Student's t-test) for normally distributed data, and nonparametric testing (Mann-Whitney U test or Kruskal-Wallis test) for non-normally distributed data. These data will include pre-intervention Hb, post-intervention Hb, and duration of oral iron treatment (days).

Pre- and post-intervention Hb for the patient with IDA will be assessed by a paired t-test if data are normally distributed, and if data are not normally distributed then the data will be analyse using Wilcoxon ranked sum test.

Is there a statistically significant difference in pre and post intervention Hb in the IDA patients after adjusting for baseline haemoglobin?

The proposal is to use a mixed effect regression model. The final model will depend on the distribution of the outcome variable (post-intervention Hb). If the outcome is normally distributed, a linear mixed effect model will be used. If the outcome is not normally distributed, different approaches can be used depending on how skewed the outcome is e.g. Generalised Linear Mixed Effect Model

7. Study organisation and management

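### The sample size section supports screening 420 children, but the plan is 1110 screened and 44 with iron deficiency anaemia; nothing visible links the two, and the 176-pair power figure fits no planned test

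*Combined protocol and SAP*

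**What the plan says.** All references are to the combined protocol and SAP.

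- **5.10 Sample size calculation** estimates a single proportion (46.2% anaemic, margin 0.05) and adds 10% for drop-out, giving 420 children to finger-prick. It then asks "Given a sample size of 420 patients allowing for 10% drop-out approximately how many anaemic patients will be enrolled" and answers about 176.
- **5.10 Power analyses** first asks "What effect size could we expect to find statistically significant for the whole cohort given an estimated sample size of 176 patients", and gives d of about 0.21 for a paired t-test. It then tabulates the IDA subgroup "given an estimated sample size of 176 anaemic patients, if the incidence of IDA is unknown": 35, 53, 70 or 88 children at IDA shares of 0.2 to 0.5.
- **6.7** says "The total patients planned to be recruited for screening is 1110 patients and these will be divided across 7 sites". Its site table has a column headed "Estimated number of patients with IDA", which totals 44.
- **6.8** requires "Reasonable potential to recruit 1110 individuals to the study over a cumulative 9-month period". The Summary and 6.14 also give 1110.
- **5.11** says "Pre- and post-intervention Hb for the patient with IDA will be assessed by a paired t-test if data are normally distributed". No paired test is specified for anaemic children without IDA.

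**The concern.** The section meant to justify the trial's size produces numbers the trial does not use. Neither 1110 nor 44 appears in the two 5.10 sections, and neither 420 nor 176 appears in the operational sections. The implied IDA yields also differ: the site table's rate per child screened is less than half of the lowest scenario in the power table.

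Three things are at stake. The primary outcome is the haemoglobin change in children with IDA, and no single expected count or detectable effect is stated for the 1110 plan. The only visible calculation supports consenting and finger-pricking 420 children, so an ethics reader cannot see the basis for 1110. And the d of 0.21 may be read as the sensitivity of the study, although it belongs to a comparison that is not planned.

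**Working it through.** **Inputs.** Anaemia 46.2%, z = 1.96, margin 0.05 and loss 10% (5.10 Sample size calculation); IDA shares 0.2 to 0.5 of 176 anaemic children (5.10 Power analyses); 1110 screened and 44 with IDA (6.7 table).

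**1. The plan's own figures reproduce.**
- n = p(1−p)z²/d² = 0.462 × 0.538 × 3.8416 / 0.0025 = 381.94 (printed 381.98); 382 + 38 = 420.
- 420 × 0.90 × 0.462 = 174.6 (printed about 176; 382 × 0.462 = 176.5).
- Paired t-test, noncentral t, 80% power, two-sided 0.05: d = 0.212 at 176 pairs, as printed. At 35, 53, 70 and 88 pairs, d = 0.49, 0.39, 0.34 and 0.30. The signed-rank test, with 3/π relative efficiency, gives 0.50, 0.40, 0.35 and 0.31. The printed table agrees.

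**2. IDA yield per child screened.**
- 5.10: 35/420 = 8.3% to 88/420 = 21.0%.
- 6.7: 44/1110 = 4.0%. By hospital: 12/310 = 3.9%, 6/150 = 4.0% (two hospitals), 4/100 = 4.0% (five hospitals). So a rate of about 4% is applied everywhere, but it is not stated or sourced.

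**3. Section 5.10's rates carried to 1110.** Anaemic: 1110 × 0.462 = 512.8; after 10% loss, 461.5.

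| IDA share of anaemic | IDA before loss | ÷ 44 | IDA after 10% loss | ÷ 44 |
|---|---|---|---|---|
| 20% | 102.6 | 2.33 | 92.3 | 2.10 |
| 30% | 153.8 | 3.50 | 138.5 | 3.15 |
| 40% | 205.1 | 4.66 | 184.6 | 4.20 |
| 50% | 256.4 | 5.83 | 230.8 | 5.24 |

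**4. What would give 44 from 1110.** Any one of these would do:
- an IDA share of 44/512.8 = 8.6% (no loss) or 44/461.5 = 9.5% (10% loss), against a lowest tabulated share of 20%;
- an anaemia rate of 44/(1110 × 0.9 × 0.20) = 22.0%, falling to 44/(1110 × 0.9 × 0.50) = 8.8%;
- retention of 44/102.6 = 43%, falling to 44/256.4 = 17%.

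In reverse, 5.10's rates need only 44/(0.9 × 0.462 × 0.5) = 212 to 44/(0.9 × 0.462 × 0.2) = 529 children screened to yield 44.

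**5. Detectable effect by number of pairs** (same test, power and alpha).

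| Pairs | 44 | 92 | 138 | 185 | 231 |
|---|---|---|---|---|---|
| d | 0.43 | 0.30 | 0.24 | 0.21 | 0.19 |

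For the signed-rank test at 44 pairs, d is about 0.44. With 44 pairs, the power to detect d = 0.2124 is only about 28%.

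**6. Is a paired comparison planned in all 176?** Children who do not meet the IDA criteria are told to stop iron (6.1, 6.12). Post-intervention haemoglobin is listed only for patients with IDA (6.13). The Surgical Admission CRF is assigned to the IDA cohort (6.14). The paired test and the mixed model are for IDA patients (5.11). Two passages are looser. The repeat bloods at surgery in 6.12 name no group, and 5.11 lists post-intervention haemoglobin among variables for between-group tests. Neither specifies a paired test in the whole anaemic cohort.

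**The case against.** The strongest objection is that the missing link may have been lost from the text. A figure directly after the 176 calculation is not shown, and the double asterisk on the IDA power question has no visible note. This stands as a limit: the finding concerns the visible text. The difference in yields is on the page in any case, and so is the 176-pair line.

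Next, 420 and 1110 need not conflict: 420 meets a precision target, and 1110 exceeds it, with a margin of 1.96 × √(0.462 × 0.538/1110) = 0.029. That is true, but the reason for the larger number still has to be given.

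The projection of 92 to 231 is also conditional. The 46.2% comes from an earlier surgical cohort. This trial takes elective cases only, applies exclusions and needs several weeks of iron before surgery, all of which could lower the yield. The IDA shares are scenarios for an incidence the plan calls unknown. All of this stands, so the multiples measure the unexplained gap and do not show that 44 is wrong. The documents quantify none of these filters.

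The bases may differ too: 35 to 88 are counts after loss, divided by 420 before loss. Dividing by the 378 retained gives 9.3% to 23.3%, which widens the gap.

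Finally, 44 pairs lies between the table's 35 and 53 rows, so the printed effects already bracket it. This is correct and limits the consequence for the primary analysis.

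**Conclusion.** The concern holds. The arithmetic within 5.10 is sound, but it does not lead to the numbers the trial will use. The implied IDA yield is 4.0% of children screened in 6.7, against 8.3% to 21.0% in 5.10. On 5.10's rates, 1110 screened would give 2.1 to 5.2 times the planned 44 if 44 is a count after 10% loss, or 2.3 to 5.8 times if it is before loss. These ratios assume that 46.2% anaemia and IDA shares of 20% to 50% apply to the children screened.

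If 44 is right, the effect on the primary analysis is modest: d of about 0.43, between the printed values of about 0.5 and 0.4. What is missing is the basis for 1110 and a single stated count and detectable effect. The 176-pair d of 0.21 is about half the effect detectable with 44 pairs and describes no specified analysis; that part does not depend on the content that is not visible.

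**What to change.** - Rewrite the two 5.10 sections and 6.7 as one chain from 1110 screened to expected IDA pairs, stating the anaemia rate, the IDA share of anaemic children and the loss assumed. If the figure or footnote that is not visible already does this, put it in the text.
- Give the basis for the 4% in the site table or correct the 44, and say whether it is before or after loss.
- State the detectable effect for the confirmed count: about 0.43 at 44 pairs, or about 0.30 to 0.19 at 92 to 231.
- Mark the 176-pair line as not applying to the primary IDA analysis, or remove it.

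The cost is text only. Enrolment, procedures and data collection do not change.
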